3 STUDY DESIGN

AVATAR-AF is a multicentre, randomised controlled study comparing a streamlined AVATAR-protocol ablation procedure to anti-arrhythmic therapy in patients with documented paroxysmal AF who are considered to be failing current strategy for AF. A secondary control arm will also compare the AVATAR-protocol to conventional AF ablation. 321 patients who are on no prior anti-arrhythmic, 'pill-in-pocket' or taking regular anti-arrhythmics will be randomised in a 1:1:1 manner to a treatment strategy of either AVATAR-protocol ablation, anti-arrhythmic therapy or conventional AF ablation and followed-up for 1 year.

The study will be conducted in accordance with the protocol, Good Clinical Practice (GCP) and all applicable regulatory requirements.

4 Endpoints

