11.2 Data Analysis

Primary outcome: Failure is counted when a patient experiences any hospital episode related to treatment for atrial arrhythmia. Patients are censored from their treatment group when they switch to a treatment other than that to which they were originally assigned or when they leave their treatment group without having experienced a hospital episode.

Data will be analyzed using the intention-to-treat principle and a p value of 0.05 or less will be considered significant. Primary outcome will be analysed using Kaplan-Meier statistics and differences will be tested using log-rank test and proportional hazards models. Other outcomes will be compared using t-test for continuous and Chi-square test or Fisher exact test for categorical variables and the appropriate generalized linear model will be used.

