5.5. Sample Size

In this time-to-event study of hospital episodes, required sample numbers have been estimated using the log-rank test under the Freedman method based on the occurrence of first event during the 12-month follow-up period. The null hypothesis is that there is no difference in the distributions. Adopting a conservative approach, an initial two-sided alpha of 0.05 is chosen, given the need to allow for the inherent multiple testing between the three arms of the study, the conservative Bonferroni correction is applied and the alpha value used in the power calculations is reduced to 0.025.

Estimating the proportion experiencing a hospital episode in the follow-up period in the anti-arrhythmic arm as 0.63 and the corresponding proportion in the AVATAR ablation arm as 0.40, assuming the occurrence of 103 events, with 100 evaluable patients in each of the two treatment arms yields a power of 0.80. A similar power is obtained for the comparison of the AVATAR ablation arm (0.40) and the conventional AF ablation arm (0.20).

A sensitivity analysis indicates that these sample size estimates are reasonable. It is anticipated that the loss to follow-up will be small, approximately 7%. Consequently, 321 patients will be randomised in a 1:1:1 manner to a treatment strategy of either AVATAR protocol ablation, anti-arrhythmic therapy or conventional AF ablation and followed-up for 1 year.

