8.2. Primary Endpoint Analysis

Failure is counted when a patient experiences any hospital episode related to treatment for atrial arrhythmia. Time to failure will be taken as the time from 1st Intervention to the time of event.

Data will be analysed using the intention-to-treat principle and a p-value of 0.025 or less will be considered significant. Primary outcome will be analysed using Kaplan-Meier statistics and differences between treatment arms will be assessed using log-rank testing and proportional hazards models. Models containing one or more of the following covariates may also be assessed if deemed necessary; site, weight, hypertension, number of anti-arrhythmic taken by patient prior to 1st intervention.

Primary endpoint analysis will be carried out between AVATAR-AF Ablation and the Anti-Arrhythmic drug treatment arm in order to investigate the primary objective. The secondary objective will be assessed by testing AVATAR-AF Ablation against the Conventional Ablation arm.

An additional per-protocol analysis will be carried out in conjunction with the above.

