Treatment Arm	Events Observed	Events Expected
Total		

Chi2(1) = x.xxx

Pr>chi2 = 0.xxx

*4.2.1 – Comparison between AVATAR-AF and Anti- Arrhythmics

*4.2.2 – Comparison between AVATAR-AF and Conventional Ablation

Table 4.3: Cox proportional hazards model investigating occurrence of AF related hospital visits*

Variable	Obvs	Mean	SD	Min	Max
Time to Endpoint	xxx	xx.x	xx.xx	xx	xx
Endpoint Occurred	xxx				
Treatment	xxx				
_st	xxx				
_d	xxx				
_t	xxx				
_t0	xxx				

_t	Haz. Ratio	SE	z	P> z	95% CI
Treatment	x.xxx	x.xxx	x.xx	0.xxx	x.xxx x.xxx

*4.3.1 – Comparison between AVATAR-AF and Anti- Arrhythmics

*4.3.2 – Comparison between AVATAR-AF and Conventional Ablation

SECONDARY ENDPOINTS

Table 5.1: Listing of deaths or strokes from any cause.

Treatment Arm	Subject Number	Type of Event	Date/Time of Event	Time to Event	Cause of Event	Relation to Treatment	Comments

Table 5.2: Log-rank test investigating occurrence of deaths and strokes*

Treatment Arm	Events Observed	Events Expected
Total		

Chi2(1) = x.xxx

Pr>chi2 = 0.xxx

*5.2.1 – Comparison between AVATAR-AF and Anti- Arrhythmics

*5.2.2 – Comparison between AVATAR-AF and Conventional Ablation

Table 5.3: Cox proportional hazards model investigating occurrence of deaths and strokes*

Variable	Obvs	Mean	SD	Min	Max
Time to Endpoint	xxx	xx.x	xx.xx	xx	xx
Endpoint Occurred	xxx				
Treatment	xxx				
_st	xxx				
_d	xxx				
_t	xxx				
_t0	xxx				

_t	Haz. Ratio	SE	z	P> z	95% CI
Treatment	x.xxx	x.xxx	x.xx	0.xxx	x.xxx x.xxx

*5.3.1 – Comparison between AVATAR-AF and Anti- Arrhythmics

*5.3.2 – Comparison between AVATAR-AF and Conventional Ablation

Table 5.4: Listing of complications arising from therapy.

Treatment Arm	Subject Number	Type of Event	Date/Time of Event	Time to Event	Cause of Event	Relation to Treatment	Comments

Table 5.5: Log-rank test investigating occurrence of complications*

Treatment Arm	Events Observed	Events Expected
Total		

Chi2(1) = x.xxx

Pr>chi2 = 0.xxx

*5.5.1 – Comparison between AVATAR-AF and Anti- Arrhythmics

*5.5.2 – Comparison between AVATAR-AF and Conventional Ablation

Table 5.6: Cox proportional hazards model investigating occurrence of complications*

Variable	Obvs	Mean	SD	Min	Max
Time to Endpoint	xxx	xx.x	xx.xx	xx	xx
Endpoint Occured	xxx				
Treatment	xxx				
_st	xxx				
_d	xxx				
_t	xxx				
_t0	xxx				
_t	Haz. Ratio	SE	z	P> z	95% CI
Treatment	x.xxx	x.xxx	x.xx	0.xxx	x.xxx x.xxx

*5.6.1 – Comparison between AVATAR-AF and Anti- Arrhythmics

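### The SAP's primary comparison is unadjusted in effect, its named covariates are left to an unspecified later choice, and the 0.025 threshold is tied to no single test

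*SAP*

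**What the plan says.** SAP 8.2 gives the methods for the primary endpoint as a pair: "differences between treatment arms will be assessed using log-rank testing and proportional hazards models". It sets the threshold as "Data will be analysed using the intention-to-treat principle and a p-value of 0.025 or less will be considered significant". It then says: "Models containing one or more of the following covariates may also be assessed if deemed necessary; site, weight, hypertension". The fourth item on that list is the number of anti-arrhythmic drugs taken before the first intervention. A per-protocol analysis is to run alongside.

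The output shells in SAP 8.7 are a log-rank table (4.2) and "Table 4.3: Cox proportional hazards model investigating occurrence of AF related hospital visits". The coefficient part of Table 4.3 has one row, for treatment. There is no shell for an adjusted primary model.

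On alpha, SAP 5.5 says "an initial two-sided alpha of 0.05 is chosen" and, after a Bonferroni correction, "the alpha value used in the power calculations is reduced to 0.025". The SAP's v1.1 change entry explains that only two pairs of arms are analysed.

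On case mix, Protocol 3 enrols patients on no earlier anti-arrhythmic, on pill-in-pocket treatment, "or taking regular anti-arrhythmics will be randomised in a 1:1:1 manner to a treatment strategy". Randomisation is stratified by site only (Protocol 5.4, SAP 5.7).

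Protocol 11.2 names the same two methods for the primary outcome and no covariates. Its threshold differs: "a p value of 0.05 or less will be considered significant". That mismatch is a separate matter.

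**The concern.** Three things are left open in SAP 8.2: which test decides each objective, whether it is adjusted, and for which covariates. No criterion, date or decision-maker is given for judging adjustment necessary. Treatment is un-blinded, and SAP 8.6 allows primary endpoint reports for the DSMB during the trial, so the wording does not rule out a choice made once outcomes are known.

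Two consequences follow. In a survival comparison, leaving out baseline variables that predict outcome costs power, and the SAP has itself picked out such candidates in a population of mixed treatment history. Also, the Bonferroni split is used up by the two arm comparisons, so nothing is reserved for several models within one comparison.

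**Working it through.** **Inputs.** From SAP 5.5: 12-month event proportions 0.63 (drugs), 0.40 (AVATAR) and 0.20 (conventional), 100 evaluable patients per arm, 103 events, two-sided alpha 0.025, stated power 0.80, log-rank test by the Freedman method. From the Protocol summary: 13 sites. Assumed, because the documents do not give it: the SD of the covariates' combined log-hazard score.

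**1. The plan's own power figure, unadjusted.** Power = Φ(√D × (1 − HR)/(1 + HR) − z), with z = 2.241 at two-sided 0.025.

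- AVATAR v drugs: HR = ln(0.60)/ln(0.37) = 0.514 and D = 200 × 0.515 = 103. Then √103 × 0.3212 − 2.241 = 1.018, so power is 0.846. Schoenfeld's formula gives 0.872.
- AVATAR v conventional: HR = ln(0.80)/ln(0.60) = 0.437 and D = 200 × 0.30 = 60. Then √60 × 0.392 − 2.241 = 0.795, so power is 0.787. Schoenfeld's formula gives 0.833.

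The stated 0.80 for the first comparison is not reproduced at 0.025; the stated inputs give 0.846. It fits an alpha of 0.017 (0.809). The present point does not depend on this.

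**2. The alpha budget.** Two independent comparisons at 0.025 give 1 − 0.975² = 0.0494. The 0.05 is spent on the two arm comparisons.

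**3. Power with pre-specified adjustment.** Both simulations below hold the marginal proportions at the planned values and test at two-sided 0.025. Simulation A uses exponential times, a log-normal frailty of the given SD, censoring at 12 months and 3,000 replicates. Simulation B is a separate run of the same quantities. Entries are unadjusted → adjusted power.

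| Assumed SD | A: 0.63 v 0.40 | B: 0.63 v 0.40 | A: 0.40 v 0.20 | B: 0.40 v 0.20 |
|---|---|---|---|---|
| 0 | not run | 0.87 → 0.87 | not run | 0.82 → 0.81 |
| 0.3 | 0.87 → 0.89 | 0.86 → 0.88 | 0.81 → 0.82 | 0.80 → 0.82 |
| 0.5 | 0.87 → 0.91 | 0.87 → 0.92 | 0.80 → 0.83 | 0.82 → 0.85 |
| 0.7 | 0.86 → 0.95 | 0.87 → 0.96 | 0.81 → 0.88 | 0.80 → 0.86 |

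The largest gain is 0.95 − 0.86 = 0.96 − 0.87 = 9 points for the first comparison, and 0.88 − 0.81 = 7 points for the second. At SD 0 there is none. Type I error of the adjusted test was 0.026 in A and 0.021 to 0.030 in B (Monte Carlo SE about 0.005).

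Simulation C (0.63 v 0.40; 200 patients in 13 sites) let site, weight, hypertension and number of earlier drugs contribute equally to the score. It compared the log-rank test with a Cox model holding the three patient-level covariates. At SD 0, 0.3, 0.5, 0.8 and 1.0, power went from 0.870, 0.872, 0.887, 0.890 and 0.883 to 0.863, 0.881, 0.912, 0.946 and 0.968. The gain at a given SD is smaller here because this model does not recover the part of the score due to site.

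**4. Smallest p-value over the optional models, no true effect.** Over the 8 subsets of the three patient-level covariates, the chance that at least one p-value reaches 0.025 was 0.037 to 0.053 in A and 0.028 to 0.045 in B. In C, the log-rank test plus all 16 subsets including site gave 0.043, 0.055 and 0.107 at SD 0, 0.5 and 1.0. The C figures are not carried forward: the full model with site as 12 indicator terms itself rejected at 0.0255 to 0.038, which adds to them, and SD 1.0 lies beyond the range used here.

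**The case against.** **A reader might infer that the primary comparison is underpowered because it is unadjusted.** The documents do not support that. The trial was sized on an unadjusted log-rank test, and at the stated inputs that test has 0.846 power (Freedman), above the 0.80 target. The documents also never call the covariates prognostic. At SD 0.3 the gain is only 1 to 2 points, and A may be a best case if the adjusted model contains the whole frailty term with nothing missing. All of this stands, and it limits the power argument to a conditional one.

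**A reader might infer that success in any one model suffices, so that the plan's error rate is inflated.** The documents do not say so. Covariate models are described as additional and optional, which reads most naturally as supportive, and the shells point to the unadjusted analyses. The inflation is a worst case. What remains is that the supportive reading is nowhere written down and that two unadjusted methods share the threshold unranked.

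**Moving the decision to a Cox model leans on proportional hazards**, and failure to enter the discharge protocol at Week 12 counts as an event (SAP 7.1), so events may cluster. This is weak: an unadjusted Cox test is essentially the log-rank test (0.866 and 0.870 in simulation C at SD 0).

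**A model with the three patient-level covariates alone would omit site, the only stratification factor.** This stands, and the fix includes site.

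**Availability of the covariates is partly inferred.** Weight and past cardiovascular medication are listed in SAP 7.4. Hypertension has no row in Table 3.1 and would have to come from medical history.

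**Conclusion.** The point holds in a limited form. SAP 8.2 and Tables 4.2 and 4.3 describe an unadjusted comparison, leave adjustment for the SAP's own covariates to a later choice, and attach 0.025 to no single analysis.

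- Pre-specified adjustment is worth roughly 0 to 9 points of power for an assumed combined log-hazard SD of 0 to 0.7. The SD is an assumption with no figure in the documents behind it.
- AVATAR v drugs does not need the gain to meet its target (about 0.85 to 0.87 unadjusted). It is more useful for AVATAR v conventional, where unadjusted power is about 0.79 by Freedman and 0.80 to 0.82 by simulation.
- If the smallest p-value were reported, the per-comparison type I error could reach about 0.03 to 0.05 instead of 0.025. This bounds what the wording leaves open; it does not estimate what the plan will do.

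The change is worth making because it removes the ambiguity at almost no cost, even if the covariates turn out to predict little.

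**What to change.** Before database lock, amend SAP 8.2 as follows.

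1. Name one deciding analysis for each of the two comparisons: a Cox model with treatment, number of earlier anti-arrhythmics, hypertension and weight (continuous), and with site handled in the same model, for example as strata. Judge its treatment p-value at the stated alpha.
2. Label the unadjusted log-rank test, the unadjusted Cox model, any other covariate set and the per-protocol analysis as sensitivity analyses.
3. Delete the words that allow any subset of the list and that make adjustment depend on a later judgement of need.
4. Align Table 4.3 with the deciding model, and confirm that hypertension can be derived for every patient.

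**Cost.** No new patients, visits or planned data. The hazard ratio becomes conditional on the covariates, rare missing values need a simple imputation rule, and the deciding test differs from the unadjusted log-rank used for sizing. Strata are suggested because 12 site indicators were mildly anti-conservative in simulation C. The stratified model itself was not simulated, and with about 200/13 = 15 patients per site in each comparison it may give back a little of the gain. Protocol 11.2 already allows proportional hazards models without ranking them, so an adjusted Cox model falls within it; a matching sentence there would be tidy.

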8.3. Secondary Endpoint Analysis

Time to death or stroke; time to procedural/drug-based complication and time to hospital episode resulting in change in therapy will be analysed using Kaplan-Meier statistics. Differences between treatment arms will be assessed using log-rank testing and proportional hazards models. Models containing one or more of the following co-variates may also be assessed if deemed necessary; site, weight, hypertension, number of anti-arrhythmic taken by patient prior to 1st intervention.

Secondary endpoint analysis will be carried out between AVATAR-AF Ablation and the Anti-Arrhythmic drug treatment arm in order to investigate the primary objective. The secondary objective will be assessed by testing AVATAR-AF Ablation against the Conventional Ablation arm.

Additional per-protocol analyses will be carried out in conjunction with the above.

8.4. Safety Variable Analysis

Adverse events will be summarised by treatment and severity. A separate table summarising adverse events and their relationship to study treatment will also be produced.

Serious adverse events will be listed and summarised by site, category and treatment. A separate table summarising serious adverse events and their relationship to study treatment will also be produced.

All safety variables will be summarized in the form of frequency tables for categorical variables or descriptive statistics for continuous variables. Quality-of-Life (QoL) questionnaire results will be summarised by Health State Score. Atrial Fibrillation Effect on QualiTy-of-life (AFEQT) questionnaire results will be summarised by both overall AFEQT score and subscale score derived using the formulae stated within the AFEQT Questionnaire Instruction and Scoring Manual

REFERENCES

If it is deemed appropriate, treatment effect will be assessed via t-test for continuous variables and Chi-square test or Fisher exact test for categorical variables (with the appropriate generalized linear model being used). Models containing one or more of the following covariates may also be assessed if deemed necessary: site, weight, hypertension, number of anti-arrhythmics taken by patient prior to 1st intervention. A p-value of 0.025 or less will be considered significant. Any testing for treatment effect will be carried out between AVATAR-AF Ablation and the Anti-Arrhythmic drug treatment arm in order to investigate the primary objective. The secondary objective will be assessed by testing AVATAR-AF Ablation against the Conventional Ablation arm.

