5 PATIENT RECRUITMENT

5.1 Patient Selection Procedures

Research staff will identify potential study patients against inclusion and exclusion criteria, before the Investigator determines their eligibility for participation. The Investigator will discuss the rationale for the study, study procedures, risks and benefits and all other issues mandated by the consent process. The potential participant will be offered an opportunity to participate in the study and written informed consent will be obtained if they agree. Study procedures and assessments will only be performed after written informed consent has been obtained.

At the screening visit, the patients general health will be assessed in a physical examination and recording of vital signs. The patient's medical and medication history will also be recorded.

A fasting blood sample will also be taken to exclude patients with uncontrolled diabetes or $[K^+]$ and serum creatinine outside acceptable safety ranges and the patient will be asked to complete a Quality of Life questionnaire (EQ5D) and an Atrial Fibrillation Effect on QualiTy of life (AFEQT) questionnaire. A blood test result within 6 months is acceptable. Any blood test result taken more than 6 months prior to randomisation will need to be repeated. A copy of the blood results must be filed in the patient notes. Any other routine clinical tests should be performed as per local practice.

Both the AVATAR protocol and conventional ablation procedures will be discussed with the patient and the anti-arrhythmic agent or the change in dose that would be selected as the next line of treatment would be agreed at this stage in preparation for potential anti-arrhythmic arm.

The informed consent process and all study assessments will be documented in the patient's medical notes and study case report forms.

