5.6. Schedule of Time and Events

In the 4 week period (28 days \pm 7days) between Randomisation and 1st Intervention, there will be no change to the patient's arrhythmia treatment: the treatment which the patient has been

randomised to will only occur on the date of 1st Intervention. All three treatment arms will follow the same scheduling protocol regardless of intervention.

1st Intervention will be considered baseline, all patient returning for follow-up 1 year \pm 14 days after this date. At this visit, all patients will undergo the following assessments:

- Physical Examination

- Vital signs

- Concomitant medications

- ECG

[figure not shown]
- 24 hour holter monitor tape

- EQ5D quality of life questionnaire

- Adverse Events

- Study Endpoints

- Atrial Fibrillation Effect on QualiTy of life (AFEQT) patient questionnaire

PROCEDURE	VISIT (Month)					
	SCREENING (M-0.5 \pm 14d)	1 ST INTERVENTION (M0 \pm 7 d)	WK4 REVIEW (M1 \pm 7d)	WK8 REVIEW (M2 \pm 7d)	WK12 REVIEW (M3 \pm 14d)	EOS (M12 \pm 14d)
Obtain Informed Consent	X					
Eligibility Criteria	X					
Vital Signs	X				X	X
Physical Examination	X				X	X
Medical History						
Assessment	X				X	X
Concomitant Medications	X				X	X
Fasting Blood Sample	X					
Quality of Life Questionnaire	X					X
Allocate 1 ST Intervention date	X					
Randomisation *	X					
Initiate 1 ST Intervention		X				
Allocate possible ablation 're-do' date **/†		X				
Review anti-arrhythmic medication †			X	X		
Post-ablation symptoms review **/†				X	X	
Enter Discharge Protocol					X	
Electrocardiogram						X
24-Hour Holter monitor tape						X
Echocardiogram	X					
Adverse Events		X	X	X	X	X
Study Endpoints			X	X	X	X
AFEQT patient questionnaire	X					X

* = Randomisation date to be scheduled 28d \pm 7 d from allocation of 1ST Intervention date

** = AVATAR-protocol ablation arm patients only

† = Anti-arrhythmic therapy arm patients only

^ = Conventional ablation arm patients

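### AFEQT and EQ-5D are measured at screening and month 12, but the named between-arm test is a t-test and no pre-specified model adjusts for the baseline score

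*SAP*

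**What the plan says.** **Measurement.** Both instruments are completed at screening. Protocol 5.1 states that "the patient will be asked to complete a Quality of Life questionnaire (EQ5D) and an Atrial Fibrillation Effect on QualiTy of life (AFEQT) questionnaire". SAP 5.6 lists "EQ5D quality of life questionnaire" and "Atrial Fibrillation Effect on QualiTy of life (AFEQT) patient questionnaire" among the 1-year assessments, and the visit schedules in both documents agree.

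**Status.** SAP 7.3 places the questionnaires among the safety and efficacy variables. Neither appears in the primary or secondary endpoints (Protocol 8.1 and 8.2; SAP 4 and 7.1 to 7.2).

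**Analysis.** SAP 8.4 first summarises EQ-5D by health state score and AFEQT by overall and subscale score. It continues that, on condition that this is thought appropriate, "treatment effect will be assessed via t-test for continuous variables and Chi-square test or Fisher exact test for categorical variables", together with a generalised linear model whose terms are not given. Further models with one or more listed covariates "may also be assessed if deemed necessary: site, weight, hypertension, number of anti-arrhythmics taken by patient prior to 1st intervention". The baseline value of the score is not on that list. The SAP does not say whether the t-test is applied to month-12 values or to change from screening.

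Protocol 11.2 is firmer: "Other outcomes will be compared using t-test for continuous and Chi-square test or Fisher exact test for categorical variables", again with a generalised linear model of unstated content.

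**Output.** SAP Tables 10.1 and 10.2 show baseline and month-12 summaries by arm. They have no column for a between-arm difference or its confidence interval.

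**The concern.** The screening score is already in the database and is the natural covariate for the same score a year later. A t-test on month-12 values ignores it. A t-test on change uses it, but with a fixed weight of one instead of the weight the data support. Either way the standard error is larger than it needs to be whenever the two measurements are correlated (with the exception, for change scores, of a correlation so high that the fixed weight happens to be right).

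Protocol 1.1 argues that symptoms are the reason for ablating, and the primary endpoint captures symptoms only indirectly, through hospital attendance. AFEQT and EQ-5D are the only scored patient-reported instruments that bear on the question directly, and about 100 evaluable patients per arm leaves little precision to spare. Treatment is also un-blinded. Leaving the form of the outcome, the covariates and the decision to test until later allows several analyses of the same score.

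**Working it through.** **The plan's own figure.** There is none to reproduce. The documents give no standard deviation, target difference, correlation or power for either score. The power of 0.80 in SAP 5.5 belongs to the log-rank comparison of hospital episodes and is not an input here.

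**Inputs from the documents**
- n = 100 evaluable patients per arm (SAP 5.5).
- Significance level 0.025 (SAP 8.4), taken as two-sided, so z = 2.241. Protocol 11.2 uses 0.05, but the variance ratios below do not depend on this.

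**Assumptions**
- Correlation ρ between screening and month-12 score, within arm: 0.3 to 0.6.
- Equal variance σ² at the two times. This is needed only for the change-score figures.
- Large-sample formulas, ignoring the few degrees of freedom spent on covariates.

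**Formulas (variance of the between-arm difference, relative to a t-test on month-12 scores)**
- Adjusted for the screening score (ANCOVA): 1 − ρ²
- t-test on change: 2(1 − ρ)
- ANCOVA relative to change: (1 − ρ²) / [2(1 − ρ)] = (1 + ρ)/2

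**Reference point.** The month-12 difference that a t-test detects with 80% power is (2.241 + 0.842) × √(2/100) = 3.083 × 0.1414 = 0.436 SD. For ANCOVA this is multiplied by √(1 − ρ²). ANCOVA power at 0.436 SD is Φ(3.083/√(1 − ρ²) − 2.241). The equivalent number per arm is 100/(1 − ρ²).

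| | ρ = 0.3 | ρ = 0.5 | ρ = 0.6 |
|---|---|---|---|
| ANCOVA variance / month-12 t-test | 0.91 | 0.75 | 0.64 |
| ANCOVA SE / month-12 t-test | 0.954 | 0.866 | 0.800 |
| Change-score variance / month-12 t-test | 1.40 | 1.00 | 0.80 |
| ANCOVA variance / change score | 0.65 | 0.75 | 0.80 |
| Detectable difference, SD (t-test 0.436) | 0.416 | 0.378 | 0.349 |
| Power at 0.436 SD (t-test 0.80) | 0.84 | 0.91 | 0.95 |
| Equivalent n per arm by t-test | 110 | 133 | 156 |

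If the two variances differ, the first row is unchanged, and ANCOVA still cannot have a larger large-sample variance than a change score, because it estimates the weight on the screening score.

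**Chance imbalance.** With 100 per arm the between-arm difference in the screening score has standard error √(2/100) = 0.14 SD. A month-12 t-test carries ρ times the realised difference. For a one-standard-error imbalance that is 0.3 × 0.141 = 0.04 SD to 0.6 × 0.141 = 0.08 SD. Adjustment removes this component.

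**The case against.** The strongest reply is that the plan commits to very little. SAP 8.4 treats these scores descriptively and tests only if that is judged appropriate. Both documents also mention a generalised linear model, and a linear model with a baseline term would fit that wording. This stands in part: a reader might infer that the plan fixes an unadjusted analysis, and it does not. But unnamed terms do not amount to a pre-specified adjustment, and the one list of covariates that exists omits the baseline score.

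The scores are not endpoints, and no conclusion of the trial is tied to them. Protocol 1.1 itself chooses hospital episodes over questionnaires as the objective measure. This stands, and it limits how much the point matters.

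A reader might also infer that this is the trial's only comparison of symptoms. It is not. Telephone follow-up asks about symptoms (Protocol 7.2 and Appendix 1) and is listed in SAP 7.3, and SAP Table 6.2 tabulates symptom status at week 8 for the ablation arms. The supportable statement is that these are the only scored quality-of-life instruments.

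A further tempting inference is that the t-test is biased or invalid, or that a baseline imbalance passes whole into the result. Neither follows. Under randomisation the test is unbiased, its standard error already allows for chance imbalance, and only ρ times any imbalance enters.

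Finally, the size is hypothetical: the documents supply no correlation, and 80% power is only a benchmark because the trial was not powered on these scores. That is correct, and it is why a range is shown.

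**Conclusion.** The point holds as one of efficiency and incomplete pre-specification. Two scores with baseline values are to be compared, if at all, by a t-test, and no stated model adjusts for the baseline score. At an assumed correlation of 0.3 to 0.6, adjustment would cut the variance by 9% to 36% relative to a month-12 t-test, which corresponds to standard errors 5% to 20% smaller. Relative to a change-score t-test, and with equal variances, the cut is 35% to 20%. If the correlation were zero, nothing would be gained over a month-12 t-test and almost nothing lost.

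The point does not reach the validity of the t-test, or the primary and listed secondary endpoints. Nor does it justify the same change for every continuous variable with a baseline value: vital signs and ECG intervals are mainly descriptive here, and nothing in the documents calls for modelling them.

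**What to change.** In SAP 8.4, with matching wording in Protocol 11.2, replace the t-test for the AFEQT overall score, the AFEQT subscale scores and the EQ-5D health state score. For each of the two planned comparisons, fit a linear model of the month-12 score on arm, the screening value of the same score, and site. Site belongs in the model because randomisation is stratified by it (Protocol 5.4). With 13 sites and about 200 patients per comparison, state in advance how small sites will be pooled if needed. Report the adjusted mean difference with its confidence interval alongside Tables 10.1 and 10.2.

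The cost is a few lines of SAP text and one added table column. No new data are needed and trial conduct does not change. The one extra requirement is a simple rule, fixed in advance, for patients whose screening score is missing.
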